One such assay is Decipher from GenomeDx Biosciences, a GC assay developed and validated in a post-RP setting as a predictor of eventual metastasis (Erho 2013). Studies have demonstrated independent prognostic value of this GC assay above and beyond standard clinicopathologic parameters reclassifying the clinically high-risk men tested into lower or significantly elevated risk of metastatic disease progression (Karnes 2013, Den 2014, Cooperberg 2015, Klein 2015, Den 2015, Ross 2015, Yamoah 2015). Studies have demonstrated that Decipher low risk patients can safely delay/defer treatment and avoid the adverse side effects of radiation treatment after radical prostatectomy while Decipher high risk patients can benefit from early adjuvant radiation (Den 2014, Den 2015).

In addition to clinical validation, several decision impact studies of Decipher were conducted to investigate a GC's influence on physicians' post-radical prostatectomy treatment recommendations (Badani 2013, Badani 2014, Michalopoulos 2014, Nguyen 2015).

Badani (2013) evaluated the influence on urologist treatment recommendations with GC in comparison to clinicopathologic risk factors alone for patients from a tertiary care center. This prospective, pre-post design study showed that among twenty-one high volume (i.e., mean 180 RP/year) urologic surgeons from 18 US institutions who were asked to make treatment recommendations for 24 prostate cancer patient cases post-RP, 43% changed their treatment recommendation with the addition of genomic information to standard clinicopathologic information.

To further reflect the distribution of test results and risk of metastasis among high-risk patients seen in a broader range of clinical settings other than academic centers, a prospective, multi-center, decision-impact study (ASSESS-D, Badani 2014) evaluated the effect of knowledge of the GC model on urologist treatment decision-making in a population of patients having undergone radical prostatectomy in a community-based practice. One hundred ten patient case histories were available for review by 51 urologists. Overall, 31% (95% CI: 27- 35%) of treatment recommendations changed with knowledge of GC. Treatment intensity was strongly correlated with the GC-predicted probability of metastasis ($p < 0.001$) and the GC was the dominant risk factor driving decisions in multivariable analysis (OR=8.6, 95% CI: 5.3-14.3%, $p < 0.0001$).

In a prospectively recruited cohort of high-risk post-RP subjects from community-based physicians, Michalopoulos (2014) demonstrated that those classified as GC high-risk were

significantly more likely to be treated (64.3%) than those classified as GC low-risk (4.4%). In addition, the authors demonstrated that the GC score was more influential than clinical variables on adjuvant treatment decisions. In particular, even among men at higher clinical risk (Gleason 4+3 or higher or CAPRA-S ≥ 5), a high GC score resulted in an increase in treatment recommendations. The converse is also seen among clinically low-risk subjects where a low GC score results in a reduction of recommendations for treatment.

These decision impact studies demonstrate the substantial impact a GC has on individual patient management above and beyond clinical variables or nomograms. Further, patient outcomes modeling study showed that Decipher-directed individualized care is associated with a 16% relative increase in the 10-year recurrence-free survival probability (Lobo 2015). However, the clinical utility of GC, and its relation to clinical risk factors, remains unverified in a randomized prospective trial and its ultimate benefit to patients and cost-effectiveness are unclear.

We propose a prospective, randomized trial comparing the frequency of receipt of adjuvant therapy for high-risk RP patients who undergo GC testing vs. those who do not. The study will be performed within the Michigan Urological Surgery Improvement Collaborative (MUSIC), a physician-led quality improvement consortium comprised of the vast majority of urology practices within the state of Michigan

2. Study Objectives

2.1. Primary Study Objective

To determine the impact of GC test results on adjuvant treatment decisions of high-risk post-RP patients with undetectable post-op PSA compared to clinical factors alone. Specifically, determine whether higher GC risk increases the likelihood of receiving adjuvant treatment and lower GC risk decreases the likelihood of receiving adjuvant treatment compared to subjects with similar CAPRA-S score who do not have the GC test.

2.2. Secondary Objectives

1. To determine whether the decision impact of the GC test is of benefit to patients. Specifically, is net benefit of GC use superior to those who do not have the GC test as assessed by decision curve analysis.
2. To determine whether use of the GC test results in decreased likelihood of adjuvant treatment for subjects with high CAPRA-S score (≥ 5) and increased adjuvant treatment for subjects with low CAPRA-S score (< 5). The hypothesis is that there is a non-zero interaction between GC test use and CAPRA-S.
3. To determine whether GC use is associated with earlier use of salvage therapies in CAPRA-S low risk patients and later use of salvage therapy in CAPRA-S high-risk patients.

4. To determine whether use of GC results in improved protection from BCR and metastatic progression.
5. To investigate the impact of GC use on QOL, and whether there is differential QOL impact among CAPRA-S high- and low-risk patients.
6. To determine whether collaborative-wide education and the use of CAPRA-S scores in the control group impacts rates of adjuvant radiotherapy compared to historical controls.

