7.3. Statistical Methods Supporting the Secondary Objectives

All tests will be two sided at a 0.05 significance level. Individuals who are lost to follow-up will be considered censored in time to event analyses. Treatment plans available at the time of drop-out will be considered the final treatment plans.

Secondary Objective 1: To determine whether the net benefit to subjects in the GC arm is superior to the UC arm. This will be determined by directly calculating the net benefit (Vickers and Elkin 2006) across a range of treatment thresholds, Decision Curve Analysis (DCA). DCA is a method for assessing prognostic models that incorporates clinical consequences and the potential probability thresholds at which the likelihood of a given outcome (eg: progression to metastatic disease) may influence the treatment decision of a patient and their physician. For example, one individual may choose treatment if there is a 5% chance of a given outcome while another individual may not be influenced unless the likelihood of that outcome is as high as 10 or 15%. Thus, this methodology allows for how different patients may differentially weigh false negative or false positive results. The calculated net benefit is plotted against threshold

probabilities, and different prediction tools (eg. CAPRA-S and GC) can be compared across these probabilities. If GC is not superior to UC across all thresholds, the region of superiority will be evaluated to determine if it contains a clinically meaningful ratio of harm due to unnecessary treatment versus missed treatment.

Secondary Objective 2: To determine whether use of the GC test result results in decreased likelihood of treatment for CAPRA-S high and increased likelihood of treatment for CAPRA-S low, a modeling approach similar to that of supporting the Primary Objective will be used, but with a GC-by-CAPRA-S interaction term as follows:

$$\text{logit}\left(\frac{\pi_{ijk}}{1-\pi_{ijk}}\right) = \beta_0 + \beta_1 G_i + \beta_2 (G_i * GC_i) + \beta_3 CAPRA-S_i + \beta_4 (G_i * CAPRA_i * GC_i) + \gamma_j + \phi_k$$

where parameters are defined as previously. The test of $H_0: \beta_4 = 0$ will be performed using a Type III test (SAS PROC GLIMMIX). The direction of the interaction will be evaluated graphically with the probability of treatment based on the model and for empirical probabilities using pre-defined GC and CAPRA-S cutoffs.

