7.5. Simulation settings

In order to determine plausible values of the parameters of the model described in Section 7.1, several clinical utility studies of the GC were pooled and utilized in a re-sampling routine to determine likely values of parameters for the current study. Although none of the previous clinical utility studies were randomized comparative trials, the DECIDE (Badani 2013), ASSESS-D (Badani 2014), and PRO-ACT Michalopolous (2014) studies did involve real high-risk patient cases (only those that were pT3 or SM+ are included here) from community and tertiary care facilities and can be expected to provide similar clinical and genomic characteristics to those eligible for this trial. In all studies, treatment recommendations were provided by physicians initially without GC risk scores then (in a blinded fashion) with knowledge of both clinical and GC risk.

There are a total of 530 recommendations with and without GC available from these clinical utility studies. To approximate a parallel-group (GC and UC) randomized trial, for each run of the re-sampling routine, the data was randomly halved, taking half of the recommendations made with knowledge of the GC ($n = 265$) and the other half with recommendations made without knowledge of the GC ($n = 265$). Ten-thousand such data sets were generated and to each, a generalized linear model of the probability of treatment was fit, similar to that described in Section 7.1 but involving only the fixed effects. Across these 10,000 samples, the mean ORs of GC score, CAPRA-S score, and arm (GC vs UC) are, respectively, 1.47, 1.15, and 0.24. The overall rate of adjuvant treatment of CAPRA-S high-risk patients in MUSIC clinics is ~8%.

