7.5.1 Power and Sample Size Simulation

Generating CAPRA-S and GC Scores

Simulation was used to determine the sample size necessary to have adequate power to reject the null hypothesis, $H_0: \beta_2 = 0$, based on the model in Section 7.1. CAPRA-S and GC risk scores for the simulated datasets were based on the distributions observed in the PRO-ACT clinical utility study (Michalopolous 2014). The distribution of CAPRA-S risk in PRO-ACT clinical is similar to that of MUSIC (62.7% vs 55.8% low risk and 44.2% vs 37.3% high risk). The distribution of GC risk scores among MUSIC patients is unknown, but due to the similarity in CAPRA-S scores, it is assumed that it will also be somewhat similar to PRO-ACT.

To ensure a) the GC score distribution is comparable to PRO-ACT, b) the CAPRA-S risk distribution is as similar as possible to MUSIC, c) the true variability of the continuous GC score, and d) the underlying correlation between GC and CAPRA-S risk is maintained, the following procedure was used to generate GC and CAPRA-S scores for each simulated individual:

1. A random percentile is generated (0-100%) and rounded to the nearest 5%.
2. PRO-ACT scores with GC score (and corresponding CAPRA-S score) within that percentile range (eg: 20-25th percentile) are then selected.
3. A GC score is then generated as a uniform a random number between the maximum and minimum of the selected PRO-ACT GC scores.
4. An initial CAPRA-S score is then randomly sampled from the selected CAPRA-S scores. The initial CAPRA-S score is then incremented by 1-point (to a maximum of 12) with 75% probability to up-adjust the slightly lower risk in PRO-ACT.

Generating Enrollments

Based on data available from MUSIC-central, the peak performing clinical centers exceeded 10 radical prostatectomy cases per month, with case-loads below 5 per month for the 4th and 5^h centers. Enrollments per site*month were generated using a Poisson process using the following conservative means: Site 1: 10, Site 2: 10, Site 3: 5, Site 4: 5, Site 6-8: 4, Site 9 and higher: 2.

Sites were randomized to enroll subjects to the GC or UC arm for each period using a fixed-block size enrollment (2, 3, or 4 depending on the randomization ratio of the simulation). Period length varied from month to year.

Intra-Class Correlations

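### Secondary Objective 2 claims opposite effects in two CAPRA-S strata, but its hypothesis is only a non-zero interaction, which a change in one stratum alone can produce

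*Combined protocol and SAP*

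**What the plan says.** Section 2.2, item 2, makes two directional statements: that "use of the GC test results in decreased likelihood of adjuvant treatment for subjects with high CAPRA-S score" (5 or more), and that there is "increased adjuvant treatment for subjects with low CAPRA-S score" (below 5). It then gives one hypothesis for both: "The hypothesis is that there is a non-zero interaction between GC test use and CAPRA-S".

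Section 7.3 applies a general rule: "All tests will be two sided at a 0.05 significance level". For Objective 2 it extends the primary model by one term, "\beta_4 (G_i * CAPRA_i * GC_i", the product of arm, CAPRA-S and GC score. It tests that coefficient with a Type III test. On direction it says: "The direction of the interaction will be evaluated graphically with the probability of treatment based on the model", together with empirical probabilities at pre-defined cutoffs.

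The descriptive paragraph that closes Section 7.1 plans treatment rates with 95% CIs by CAPRA-S and GC category, and predicted probabilities with CIs for combinations of the two. It names no GC-versus-UC comparison within a CAPRA-S stratum.

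**The concern.** An interaction is a difference between two arm effects. It can be non-zero when only one stratum responds, and it does not establish the sign of either effect. The objective needs both signs. Between the two stands only a visual check, with no within-stratum contrast, no required sign and no rule for when the objective counts as met.

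The likely error is a one-stratum effect reported as a two-way redistribution of treatment: GC use shown to spare clinically high-risk men and to intensify care in clinically low-risk men, when only one half has support. That two-part statement would be a prominent message of the trial, so the test should match it.

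**Working it through.** **1. Stated figure.** The plan gives no power or sample size for Objective 2. The 83% in Section 7.5.2 is for the primary coefficient at 350 subjects and does not bear on this point.

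**2. Logic.** Let dH and dL be the GC-versus-UC log odds ratios at CAPRA-S ≥5 and <5.
- Objective: dH < 0 and dL > 0.
- Hypothesis: dH − dL ≠ 0.

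The first implies the second. The second does not imply the first: dH = 0 with dL > 0, or dH < 0 with dL = 0, satisfies it.

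**3. Inputs for an illustration.**
- 550 subjects (Section 3), split 1:1, so 275 per arm.
- 44.2% CAPRA-S high (Section 7.5.1). The sentence there lists its pairs in inconsistent order. 44.2% is read as MUSIC because the simulation adjusts PRO-ACT scores upward. This gives 275 × 0.442 ≈ 122 high and 275 × 0.558 ≈ 153 low per arm.
- Usual-care rate 8% in high men (Section 7.5). The low rate is not given; 4% is assumed.
- Clustering and period effects ignored.

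Test: z = (dH − dL) / √(sum over the four arm-by-stratum groups of 1/treated + 1/untreated), two-sided 0.05.

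**4. One case by hand** (only low men change, 4% to 12%).
- dH = 0; dL = ln(0.12/0.88) − ln(0.04/0.96) = 1.186.
- Variance = 2/(122 × 0.08 × 0.92) + 1/(153 × 0.04 × 0.96) + 1/(153 × 0.12 × 0.88) = 0.223 + 0.170 + 0.062 = 0.455; SE = 0.674.
- Power ≈ Φ(1.186/0.674 − 1.96) = Φ(−0.20) = 42%. Simulation gives 40%.

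**5. Simulation** (40,000 trials per row, 0.5 added to each cell).

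| Truth | High, UC→GC | Low, UC→GC | Interaction significant | Significant, and point estimates in claimed pattern | Both stratum contrasts significant as claimed |
|---|---|---|---|---|---|
| Only high changes | 8→2% | 4→4% | 27% | 23% | 0.6% |
| Only low changes | 8→8% | 4→12% | 40% | 31% | 1.2% |
| Only low changes | 8→8% | 4→15% | 58% | 39% | 1.6% |
| Claimed pattern | 8→2% | 4→12% | 90% | 89% | 35% |

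In the first three rows Objective 2 is false. The fifth column matters most: there the flat stratum drifts the right way by chance and the plot looks like the claim.

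The figures are approximate. A 2% rate means 122 × 0.02 = 2.4 expected events, and about 9% of tables in those rows have an empty cell. Without the 0.5 correction, counting such tables as non-significant, the one-stratum rows give 24% to 59% and the claimed row 82%.

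**6. The term actually tested.** In the Section 7.3 model the arm log odds ratio is β1 + GC × (β2 + β4 × CAPRA-S). β4 describes how the GC-score slope in the GC arm varies with CAPRA-S. It is not the interaction of GC use with CAPRA-S named in Section 2.2, and the model has no two-way arm-by-CAPRA-S term. A non-zero β4 fixes neither sign. With values chosen only to show this (β1 = −1.43, β2 = 3.85, β4 = −0.3, GC score 0.4):
- CAPRA-S 3: −1.43 + 0.4 × (3.85 − 0.9) = −0.25.
- CAPRA-S 7: −1.43 + 0.4 × (3.85 − 2.1) = −0.73.

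Both effects are downward. The percentages in step 5 therefore illustrate the Section 2.2 hypothesis; they are not operating characteristics of the fitted model.

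**The case against.** The best defence is that direction is not ignored. Section 7.3 requires it to be examined with both model-based and empirical probabilities, and Section 7.1 adds rates and predicted probabilities with CIs. This defence holds against gross misreading. A reader might infer that a fully reversed pattern could pass as success because the test is two-sided. The documents do not support that worry. With high men going from 8% to 16% and low men from 4% to 3%, the interaction is significant in 28% of simulated trials, but essentially none has point estimates in the claimed pattern. The planned displays would expose it. They do not protect against the one-stratum case.

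A reader might also infer that the plan's own planning values predict the reverse of Objective 2, since "the mean ORs of GC score, CAPRA-S score, and arm (GC vs UC) are, respectively, 1.47, 1.15, and 0.24" and the simulation states that "the underlying correlation between GC and CAPRA-S risk is maintained". That inference needs a unit for the 1.47, a GC-score distribution and a positive correlation, and none of these is given. If 1.47 is per full 0–1 unit, with an assumed GC mean of 0.30–0.45, SD 0.2 and correlation 0.2–0.4, the stratum odds ratios are about 0.28–0.30 (low) and 0.30–0.32 (high), essentially no reversal. If it is per 0.1 but the correlation is zero, the high-to-low ratio is 0.96–0.98. The Section 7.1 model also has no arm-by-CAPRA-S term, so it was never a planning model for this objective.

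Finally, this is a secondary objective with no stated power. Insisting that both contrasts reach significance would leave about 35% power even under a large true effect. That is a fair reason not to make such a rule the sole criterion for reporting the objective.

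**Conclusion.** The point stands: the hypothesis in Section 2.2 is weaker than the objective it serves, and the graphical check in Section 7.3 does not close the gap when only one stratum changes. That conclusion is logical and does not depend on the scenario rates. Its illustrative size, about 27% to 58% of trials significant and 23% to 39% also resembling the claim, rests on the assumed 4% low-stratum rate, the chosen changes, the 44.2% share and independence of subjects. A second mismatch, between the interaction named in Section 2.2 and the three-way term tested in Section 7.3, needs correcting in the same place. Correcting that term alone would not be enough, because a proper two-way interaction still does not establish two opposite effects. The primary analysis is unaffected.

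**What to change.** In Sections 2.2 (item 2) and 7.3:

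- Fit arm, CAPRA-S and arm-by-CAPRA-S with the center and period effects. Enter CAPRA-S as the ≥5 versus <5 indicator used in the objective. If the continuous score is kept, state how each stratum's contrast is derived from it.
- Pre-specify the GC-versus-UC odds ratio with 95% CI in each stratum.
- Claim a decrease or an increase only in a stratum whose interval supports it, and the full two-part pattern only if both do.
- Keep the interaction p-value as supportive evidence of effect modification, and the graphs as description.

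Alternatively, keep an interaction as the main test, make it the arm-by-CAPRA-S term, and reword Objective 2 as effect modification by CAPRA-S with no directional claim.

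The cost is SAP wording; no new data are needed. The two-part claim becomes harder to support: about 35% against 90% for the interaction alone (82% without the 0.5 correction) if rates truly move from 8% to 2% and from 4% to 12%. The plan should say that the objective is not powered.

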3.4. Clinical Data Collection

Where available, participating physicians in the study will be asked to provide the following clinicopathologic data in the provided case report form (CRF) for subjects meeting the inclusion criteria below. All data submitted to GenomeDx will utilize a case ID number and will be de-identified by the site prior to submission.

1. Ethnicity
2. Age at radical prostatectomy
3. Pre-operative PSA level: last pre-operative PSA level before radical prostatectomy
4. Lymph node status
5. Clinical and pathological stage
6. Clinical and pathological Gleason score (primary, secondary, and tertiary pattern if available)

7. Surgical margin status
8. Extra-prostatic extension
9. Seminal vesicle invasion
10. All available post-op PSA levels
11. Recommended treatment or management option for the patient after surgery
(detailed by type of treatment recommended)
12. Dates of actual treatments
13. Patient outcome

[figure not shown]

Figure 1: Study flow diagram

[figure not shown]

Figure 2: Patient flow timeline

4. Subject Eligibility

4.1. Inclusion Criteria:

Individuals satisfying all of the following criteria will be eligible to participate.

1. Prostate cancer patients who have undergone radical prostatectomy(RP)
2. PSA <0.1 ng/ml at enrollment
3. At least one of the following:
 - a. pT3 (SVI or EPE), **or**
 - b. Positive Surgical Margins
4. Tumor tissue (FFPE block) available for processing
5. RP within 1 year of enrollment
6. 18 years of age or older

4.2. Exclusion Criteria:

Individuals who satisfy **any** of the following criteria will not be eligible to participate.

1. Have regional or distant metastatic disease
2. Received any radiation or hormone therapy (neo-adjuvant, adjuvant, or salvage)
3. Node positive
4. Subjects who do not have banked specimens

5. Endpoints

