5.2. Secondary Endpoints

The following secondary endpoints will be utilized:

1. Time (from randomization) to adjuvant treatment administration
2. Time (from randomization) to salvage treatment administration
3. Biochemical Recurrence (BCR) at 3 years
4. Metastatic disease (regional or distant) at 3 years
5. QOL measures currently collected as part of the MUSIC-PRO initiative (<http://musicurology.com/pro/>) at 3, 6, 12, and 24 months after surgery

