Secondary Objective 3: Time-to salvage therapy initiation will be modeled using a Cox formulation of a Frailty regression model with a similar formulation (ie: main and random effects) to that used for the primary analysis. Kaplan-Meier curves for GC and UC arms will be plotted, as well as for combinations of high- and low-risk GC and CAPRA-S groups.

Secondary Objective 4: Time-to BCR and metastatic progression will be evaluated similarly to the model described for Secondary Objective 3.

Secondary Objective 5: Summary statistics for all QOL instruments and corresponding confidence intervals will be calculated and compared for the GC and UC subjects and shown graphically over time. Validated instruments are used to measure erectile function, urinary function, sexual interest, and sexual satisfaction. Scores for each domain will be scaled with a minimum to maximum range of 0-100. Comparisons between GC and UC subjects will be made at each timepoint (3, 6, 12 and 24 months after surgery) and on each domain and overall score (VAS 0-10), using an ANCOVA analysis including adjustment for time since surgery. Should the assumptions for ANCOVA not be met (strongly skewed data or substantial ceiling or floor effect) a semiparametric ANCOVA model will be used (as in Buja 1989) to adjust for time-from surgery. If the distribution of time-from surgery is similar in the two groups, a Mann-Whitney test for differences will be used to corroborate the ANCOVA model. For this secondary objective, there will be no adjustment for multiple comparisons across domains or time points.

Exploratory Objective: Using a variety of budget models the cost of care for patients in the GC vs. UC arms will be compared out to 3 years from surgery. This will include estimated costs for adjuvant therapy. Differences in total cost, and differential cost per patient (UC vs GC) will be calculated and compared using either standard t-tests if data is normally distributed or appropriate non-parametric test if data is right skewed.

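### Secondary Objective 3 asks about the timing of salvage, but time from randomization to salvage mixes how many men recur with how promptly recurring men are treated

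*Combined protocol and SAP*

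**What the plan says.** Section 2.2, Objective 3, is a hypothesis about timing with opposite directions by clinical risk: "earlier use of salvage therapies in CAPRA-S low risk patients and later use of salvage therapy in CAPRA-S high-risk patients".

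Section 5.2 supplies one endpoint for it: "Time (from randomization) to salvage treatment administration". Section 7.3 supplies one analysis: "Time-to salvage therapy initiation will be modeled using a Cox formulation of a Frailty regression model", built like the primary model, plus Kaplan-Meier curves by arm and by GC and CAPRA-S risk group. The primary model in 7.1 contains arm, arm by GC score, CAPRA-S, and random center and period effects. It has no arm-by-CAPRA-S term, and 7.3 adds none for Objective 3.

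Four other statements bear on the point:

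- **Objective 4 (2.2)** expects GC use to reduce recurrence: "To determine whether use of GC results in improved protection from BCR and metastatic progression". BCR gets its own model of the same type in 7.3.
- **Eligibility (4.1)** requires PSA below 0.1 ng/ml, so no man has BCR at the start.
- **Section 5.1** defines adjuvant therapy as given before BCR (PSA 0.2 ng/ml or more) and within 18 months of prostatectomy. Salvage is not defined anywhere.
- **Section 3.4** collects treatment dates and "All available post-op PSA levels".

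**The concern.** For a man treated after recurrence, time to salvage is the sum of two parts: time to BCR, and the delay from BCR to treatment. Whether salvage is given promptly is a question about the second part. Over 3 years a man who does not recur contributes only censored time, so the hazard ratio on the planned clock depends heavily on the first part.

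The plan's own hypotheses make this matter. If Objective 4 is right and GC use lowers BCR, the salvage hazard falls in the GC arm, and the analysis shows later salvage even when recurring men are treated exactly as promptly as before. Objective 2 expects more adjuvant therapy in CAPRA-S low and less in CAPRA-S high. If adjuvant therapy prevents recurrence, salvage becomes rarer in the low stratum and commoner in the high stratum, which is the reverse of Objective 3 and has nothing to do with promptness.

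At stake is the interpretation of one secondary objective. A statement that salvage came earlier or later would rest on an analysis that cannot separate timing from incidence. The primary endpoint is unaffected.

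**Working it through.** The documents state no event count, effect size or power for salvage, so there is no planned figure to reproduce.

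**Inputs from the documents**

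- 550 men (section 3), 1:1 allocation (7.5.2), 3-year follow-up (section 3), two-sided 0.05 (7.3).
- CAPRA-S split in the collaborative: 55.8% low and 44.2% high. In 7.5.1 these are the figures that sum to 100% and fit the remark that the earlier study had slightly lower risk.
- Per arm: 550 × 0.442 / 2 ≈ 122 high; 550 × 0.558 / 2 ≈ 153 low.

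**Assumptions not in the documents:** exponential time to BCR with 3-year risk b of 20-40%; exponential delay with mean 9 months; 80% of recurring men salvaged; clustering ignored.

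**Formulas.** Let λ = −ln(1 − b)/36 and μ = 1/(mean delay), per month. The probability of salvage by 36 months is

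p = 0.8 × [1 − (μe^(−36λ) − λe^(−36μ))/(μ − λ)].

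The hazard ratio on the planned clock is approximately ln(1 − p_GC)/ln(1 − p_UC). With n men per arm, the expected number of events is d = n(p_GC + p_UC). Approximate power (Schoenfeld) is Φ(z − 1.96) + Φ(−z − 1.96), with z = (√d/2) × |ln HR|.

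**(a) Timing changes, recurrence does not (delay 9 to 4.5 months)**

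| BCR, both arms | p_UC | p_GC | HR | Power, 122 per arm | Power, 153 per arm |
|---|---|---|---|---|---|
| 20% | 0.123 | 0.142 | 1.16 | 7% | 8% |
| 40% | 0.252 | 0.287 | 1.17 | 10% | 11% |

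Simulation under the same assumptions gives 7-12% per stratum.

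**(b) Recurrence changes, timing does not (BCR 40% UC, 30% GC; delay 9 months in both)**

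p_UC = 0.252 and p_GC = 0.187, so HR ≈ 0.207/0.290 = 0.71. At 122 per arm, d = 122 × 0.4385 ≈ 53.5 and z = (7.31/2) × 0.340 = 1.24. Power is therefore about 24%. Simulation also gives about 24%, nearly all in the direction of later salvage. Time from BCR to salvage rejects in about 5% of the same trials, as it should.

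**(c) Both change (BCR 40% to 30%, delay 9 to 4.5 months)**

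p_GC = 0.214, so HR ≈ 0.83. The planned analysis points to later salvage although recurring men are treated in half the time.

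**Sensitivity.** With a different set of assumptions (550 men, all recurring men salvaged, UC BCR 15%, 25% or 40%), a recurrence hazard ratio of 0.6 with an unchanged 6-month delay gives a salvage hazard ratio of 0.60 at every BCR rate. Halving a 6-month delay gives 1.10-1.13, with 7-14% power. Halving a 12-month delay gives 1.22-1.27, with 11-35% power. The direction is stable; the sizes are not.

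**What a recurrence clock would achieve.** Under the main assumptions, time from BCR to salvage detects a halved delay in about 20-45% of trials per stratum. If the delay is halved in CAPRA-S low and doubled in CAPRA-S high, as Objective 3 envisages, it finds both halves in 6-16% of trials, against about 1% for the planned endpoint.

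**The case against.** - **Salvage need not follow BCR under this plan.** This stands. Salvage is undefined, and treatment begun before PSA 0.2 but after 18 months is outside the adjuvant definition and otherwise unclassified. A reader might infer that GC can bring salvage forward only by shortening the delay after BCR; the documents do not say so. A clock starting at PSA 0.2 would drop these early-treated men or give them negative times.
- **A general fall in BCR could not make Objective 3 falsely positive as a whole.** This also stands. The objective predicts opposite directions, and a common reduction pushes both strata toward later salvage. In simulation of case (b), the low stratum was significantly earlier in 0.03% of trials, and both halves held together in none. Pooled figures (about 45-49% at 275 per arm in case (b)) test a single direction that Objective 3 does not pose.
- **BCR is already modelled separately, and no rule declares the objective met.** True, and a careful reader could set the two results side by side. But the plan does not require this, and it names no measure of timing given recurrence.
- **The randomization clock keeps every enrolled man in the comparison.** True, and a good reason to keep it. Measures confined to men who recur or receive salvage give up that protection.
- **All sizes rest on assumed rates.** True. The mixing of incidence and timing does not.

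**Conclusion.** The concern holds in limited form. The planned endpoint combines recurrence with promptness of treatment and cannot by itself support a statement that salvage was earlier or later. Under the stated assumptions it detects a halved delay in about 7-12% of trials per stratum, and it reads a BCR reduction from 40% to 30% as later salvage in about 24% at 122 per arm. The second effect could falsely support the CAPRA-S high half of the objective and would count against the low half.

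Two stronger readings are not supported. The endpoint is not blind to timing: power is low rather than zero and reaches 35% under the most favourable setting tried. Nor could an overall fall in recurrence confirm the whole objective. For a secondary objective this is worth correcting, but it does not threaten the trial.

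**What to change.** In section 5.2 (2) and section 7.3, Objective 3:

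1. Keep time from randomization to salvage as the randomized analysis. Report it as salvage incidence, beside BCR by arm, and draw no earlier or later conclusion from it alone.
2. Add an arm-by-CAPRA-S term, since the hypothesis is of opposite effects by CAPRA-S.
3. Define salvage for analysis so that treatment begun before PSA 0.2 but after 18 months is classified. Which class it falls in is for the sponsor to decide.
4. Base any earlier or later wording on two supportive measures: last PSA before salvage, by arm within CAPRA-S strata; and time from first PSA of 0.2 or more to salvage in men with BCR, using the same center and period effects. State how men treated before PSA 0.2 are handled.

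The cost is plan wording and a small extra analysis; 3.4 already collects the PSA values and treatment dates. The downside is that both supportive measures condition on a post-enrolment event, so they are not fully randomized comparisons, and a null result would say little given their modest per-stratum power. The gain is mainly in measuring the quantity the objective names.
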